### **Aim:**

The study evaluated the effect of different doses of metformin on the intermediates of NO (nitric oxide) biosynthesis in people with pre-DM (pre-diabetes).

### **Material and Methods:**

#### *Population and groups*

The treatment-naïve patients (regarding to hypoglycemic drugs) with new-diagnosed pre-DM were recruited from Diabetes Centre between October 2017 and December 2018.

Inclusion criteria for the patients:

- Pre-diabetes based on FG (fasting glucose) and / or OGTT (oral glucose tolerance test) according to the local (similar to EASD- European Association for the Study of Diabetes) criteria
- Age 40-65 yo
- Any gender, profession, place of residence
- Negative history for diabetes
- No hypoglycemic drugs in the past
- Negative history for cardio-vascular diseases
- Written consent to participate in the study

Criteria for exclusion for the patients:

- Age <40 or >65 years
- History of diabetes –from patients, patients family and/or medical records if available
- FG>125 mg% (6.9mmol/L) and or glucose after 2 hours in OGTT >199mg% (11mmol/L)
- History of treatment with any hypoglycemic drug
- History of cardio-vascular disease
- Contraindications to the use metformin according to the Product Characteristics
- Known gastro-intestinal disease which could be potentially responsible for metformin intolerance (eg IBD- irritable bowel disease, GERD- gastro-esophageal reflux disease)

- Known potential difficulties in collaboration with patients (dementia, mental disorders, distance from patients residence if considered as potentially problematic)
- No consent to participate in the study
- Patient participation in another study

Inclusion criteria for \* healthy volunteers:

- Age 40-65 yo
- Any gender, profession, place of residence
- Negative history for diabetes, pre-diabetes and FG<100 mg% (5.6 mmol/L)
- No hypoglycemic drugs in the past
- Negative history for cardio-vascular diseases
- Written consent to participate in the study

***Methods: definitions, information collected, lab-tests performed, treatment scheme, lab-tests technique, statistical analysis***

1. Pre-diabetes diagnosis definitions:

IFG (impaired fasting glycaemia): FG (fasting glucose): 100-125 mg% (5.6- 6.9 mmol/L);

IGT (impaired glucose tolerance): glucose 140-199 mg% (7.8- 11.0 mmol/L) after 2 hours of 75 glucose solution taken

2. Negative history for cardio-vascular diseases definitions:

Patients without ischemic heart disease and/or stroke and/or PAOD (peripheral arterial occlusive disease) in a history

3. Demographic information collected: age, sex

4. Baseline parameters collected: weight, height, BMI (body mass index), information about fatty liver (based on the available ultrasonography organs' description), family history for DM (YES/NO), hypertension (YES/NO), active nicotinism (YES/NO); and biochemical: FPG, lipids profile, creatinine, AlaT (alanine transaminase), creatinine, HbA1c (glycated hemoglobin) if available.

5. Before the first dose of the metformin and after: 6, 12, 15 weeks of the treatment, the blood samples were collected for the assessment of the:

a. concentration of the metformin

b. concentration of the compounds related to the production of the NO: L-arginine, L-citrulline, ADMA – asymmetric dimethylarginine, DMA – dimethylamine, SDMA – symmetric dimethylarginine, ornithine

\* For healthy volunteers only once concentration for the compounds related to the production of the NO was assessed and no blood samples for metformin concentration were taken.

The admissible delay in taking blood for lab-testing was set at 4 days. The blood samples were taken randomly (no hours or gaps between metformin taking were defined).

6. Patients with pre-DM were treated 3 weeks with an increasing dose of the immediate-release (regular form) metformin to 3 x 500 mg, and then randomly assigned to:

group A – continuation of a dose of 3 x 500 mg or

group B – increase dose to: 3 x 1000 mg (also by titration); after 12 weeks this group returned to the dose 3 x 500 mg for the next 3 weeks

7. If potential side effects appeared in group B, the patients could take a lower dose (3 x 500 mg if well-tolerated) and thus change to group A.

8. If the smallest dosage (3 x 500mg) was not tolerated the patient was excluded from the study.

9. During titration period (by phone) and blood collection visits (personally), patients were asked about the compliance and drug's tolerance. The patients were also encouraged to contact in any case of the problem with metformin tolerance.

10. The technique used to assess concentration of the metformin in serum and the wider panel of L-arginine/NO pathway metabolites: LC-MS/MS (liquid chromatography-mass spectrometry).

11. Safety outcomes: Adverse events were reported at each clinic visit and revised via telephone contact during treatment period.

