## 12. SAP- Statistical Analysis Plan

- to prove the homogeneity of the compared groups, analysis of the baseline parameters was done
- to show the potential differences between people with pre-DM and healthy people the comparison of the baseline parameters was done
- to follow the metformin intake by the patients, the metformin concentration with its change during the therapy was done
- for the analysis of the impact of the metformin dosage on the concentration of the compounds related to the production of the NO the difference of these compounds between two groups was done
- as an extra analysis, the correlations of the serum drug concentration with BMI and body mass, after 6 and 15 weeks of the treatment was done, while research was ongoing

[figure not shown]
The Statistica 13 program was used with cut-off point for statistical significance (P) at 0.05.

The normality of the distribution of the examined quantitative variables was checked using the Shapiro-Wilk test. In order to determine the significance, statistical tests were used in accordance with the distribution of variables and the nature of the data (Student t test, Welch test, Mann-Whitney test, chi – square test, the Wilcoxon signed-rank test, Kruskal – Wallis test, Friedman test, F test). To determine the correlation the Spearman's rank-order correlation and the Pearson correlation was used.

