## The flow chart of the management of the patients

Met “Inclusion criteria”: YES; Written consent: YES

Initial visit: blood samples for: arginine, citrulline, ADMA, DMA, SDMA, ornithine

Control visit: blood samples for: arginine, citrulline, ADMA, DMA, SDMA, ornithine  
and metformin

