### Randomization

Group B

*3 weeks titration to the dose:*

*3000mg/day*

Group A

[figure not shown]
*6 weeks continuation of the dose 1500/day*

Good dose tolerance: YES

NO

*3 weeks continuation of the dose*  
*3000mg/day*

Control visit: blood samples for: arginine, citrulline, ADMA, DMA, SDMA, ornithine  
and metformin

*3 weeks continuation of the dose 1500mg/day*

Final visit: blood samples for: arginine, citrulline, ADMA, DMA, SDMA, ornithine  
and metformin

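### The A versus B dose comparison names no visit and only unadjusted tests; an ANCOVA at week 12 on the week-6 value, with patients kept as randomised, would define it and would usually be more precise

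*Combined protocol and SAP*

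**What the plan says.** The dose analysis is a single line of the SAP (section 12): for the effect of dosage on the NO-pathway compounds, "the difference of these compounds between two groups was done". It names no visit, baseline or covariate. On method, the SAP says that "statistical tests were used in accordance with the distribution of variables and the nature of the data (Student t test, Welch test, Mann-Whitney test" and others). The rest of the list is chi-square, Wilcoxon signed-rank, Kruskal-Wallis, Friedman and an unexplained F test.

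The schedule is spread over three places:

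- **Methods, item 5:** "Before the first dose of the metformin and after: 6, 12, 15 weeks of the treatment, the blood samples were collected".
- **Methods, item 6:** the description of the run-in reads "treated 3 weeks with an increasing dose of the immediate-release (regular form) metformin to 3 x 500 mg, and then randomly assigned to". The two arms that follow are A, which stays on 3 x 500 mg, and B, which titrates to 3 x 1000 mg. For group B, "after 12 weeks this group returned to the dose 3 x 500 mg for the next 3 weeks".
- **Flow chart:** the entry "Control visit: blood samples for: arginine, citrulline, ADMA, DMA, SDMA, ornithine", with metformin, stands before the Randomization box. After that box, group A has "6 weeks continuation of the dose 1500/day" and group B has 3 weeks of titration plus 3 weeks at 3000 mg/day. A second control visit follows, then 3 weeks at 1500 mg/day, then the final visit.

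On intolerance in group B, item 7 says "the patients could take a lower dose (3 x 500 mg if well-tolerated) and thus change to group A".

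**The concern.** The effect of dose on these compounds is the study's aim, yet the SAP leaves open which of four samples carries the comparison. If only one of them is taken while the groups are assigned different doses, the contrast is not defined until that visit is named.

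Each patient also has an earlier measurement of the same compound. None of the listed between-group tests for quantitative data adjusts for it, so the interval for the dose effect may be wider than it needs to be. Which earlier value may serve as covariate depends on when randomisation took place. A value taken after group B's dose began to rise would carry part of the effect being estimated.

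Finally, the SAP defines no analysis set. If B patients who step down are counted in A, the groups compared are no longer the groups randomised.

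**Working it through.** The plan states no sample size, power, effect size, SD or correlation, so it has no figure to reproduce.

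**1. When was randomisation?** Inputs: sampling at weeks 0, 6, 12 and 15 (item 5); randomisation to second control visit, 6 weeks in A and 3 + 3 = 6 in B; second control visit to final visit, 3 weeks (flow chart).

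- Counting back from the final visit: 15 − 3 − 6 = week 6. Counting forward: 6 + 6 = 12 and 12 + 3 = 15, which match item 5.
- From week 3 the later visits would fall at 3 + 6 = 9 and 9 + 3 = 12, which do not match.
- Item 6's 12 weeks before B's step-down works as weeks of treatment: 12 + 3 = 15. Counted from randomisation, the trial would end at 6 + 12 + 3 = 21 or 3 + 12 + 3 = 18.

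**2. Which sample shows the dose contrast?** With randomisation at week 6, both groups are untreated at week 0, on 1500 mg/day at week 6, and again on 1500 mg/day by week 15. Assigned doses differ at week 12 only: 1 sample of 4. Week 6 is the last sample before they diverge.

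**3. What does adjustment gain?** Let r be the within-group correlation between week 6 and week 12, and n the number per arm (equal arms). Both are assumptions. The variance of the ANCOVA estimate is, relative to:

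- a raw week-12 comparison: 1 − r² in large samples, times (2n − 3)/(2n − 4) in small ones, which is 27/26 at n = 15 and 57/56 at n = 30;
- a change from week 6, with equal variances: (1 − r²)/[2(1 − r)] = (1 + r)/2.

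| r | raw, large sample | raw, n = 15 | raw, n = 30 | change score |
|---|---|---|---|---|
| 0.3 | 0.91 | 0.945 | 0.926 | 0.65 |
| 0.5 | 0.75 | 0.779 | 0.763 | 0.75 |
| 0.7 | 0.51 | 0.530 | 0.519 | 0.85 |

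Expressed as equivalent patient numbers (1/ratio, large sample), the gain is 1.10, 1.33 and 1.96 times against the raw comparison, and 1.54, 1.33 and 1.18 times against the change score.

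Break-even against the raw comparison is r = √[1/(2n − 3)]: √(1/27) = 0.19 at n = 15 and √(1/57) = 0.13 at n = 30.

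As an illustration, take an assumed 0.6 SD difference, 30 per arm and a two-sided 0.05 level (the SAP does not state sidedness). Simulated power is about 63% unadjusted and 66%, 75% and 89% adjusted at r = 0.3, 0.5 and 0.7. ANCOVA type I error was 0.049 to 0.052.

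**4. Is it unbiased?** In a simulation with 20 per arm, r = 0.5 and a true difference of 0.80 SD, both methods averaged 0.80. The SD of the estimate was 0.279 adjusted and 0.318 unadjusted; (0.279/0.318)² = 0.77, in line with 0.75 × 37/36 = 0.77.

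**5. Why the covariate must precede randomisation.** If week 6 already carried a fraction f of the dose effect, adjusting for it would leave 1 − r·f. With f = 1 that is 0.70, 0.50 and 0.30 at r = 0.3, 0.5 and 0.7; with f = 0.5 it is 0.85, 0.75 and 0.65. On the schedule in step 1 this does not arise.

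**The case against.** **The unadjusted test is valid.** This stands. A comparison of groups as randomised is unbiased and keeps its type I error. A reader might infer that the planned tests give a wrong answer, but nothing in the documents supports that; only precision and definition are at issue.

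**The gain rests on assumptions.** This also stands. The documents give neither r nor n, and item 5 says that blood was drawn at no fixed interval from dosing, which may lower r. At r = 0.3 the gain over a raw comparison is slight. The figure of 1.96 times as many patients needs r = 0.7, for which there is no evidence here.

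**The comparator is unknown.** The SAP does not say that raw week-12 values were compared. The listed tests could have been applied to changes, so one cannot state that the week-6 value was discarded. ANCOVA still gains against a change score, but the pattern reverses: most at low r, least at high r.

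**Item 6 may look like a contradiction.** Read alone, it suggests randomisation at week 3, and a reader might conclude that the plan conflicts with itself or that week 6 is a post-randomisation value. The documents do not support this. Item 6 gives a titration length and an order of events, not a randomisation week; part of the chart is not shown and may state the run-in; and the readable durations with item 5 fit week 6 only. What remains is a short omission in item 6.

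**Conclusion.** The point holds as one of specification and efficiency. The SAP names no visit for its main comparison and no covariate-adjusted method; the F test has no stated covariate and cannot be counted as one. On the schedule that fits the sampling weeks, week 12 is the visit to analyse and week 6 the baseline.

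The gain is real only if week-6 and week-12 values correlate above about 0.13 to 0.19 (30 to 15 per arm). Over r = 0.3 to 0.7 the variance falls by 9% to 49% against a raw comparison, or by 35% to 15% against a change score. Week 6 as the point of randomisation is derived from visit order and durations; it is not printed in the readable text.

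The analysis set matters separately and concerns bias. Patients who leave the higher dose do so because of side effects. Counting them in A would make both groups depend on an event after randomisation, and covariate adjustment does not repair that. Item 7 invites this handling, but the SAP does not say whether it was used.

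**What to change.** Add to section 12:

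> The dose comparison is A versus B at week 12, with patients analysed in the group to which they were randomised, including group B patients who step down under item 7. Each compound is analysed by ANCOVA adjusted for its last pre-randomisation value (week 6), on the log scale if skewed.

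If records show that randomisation was in fact at week 3, use the pre-treatment sample as the covariate and correct the flow chart.

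In item 6, add that after titration patients stayed on 3 x 500 mg to week 6 and were randomised after the week-6 sample, and that B's 12 weeks are weeks of treatment. This is a minor clarification.

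The cost is one degree of freedom per model, with no new patients, visits or assays. Keeping step-downs in B estimates the effect of being assigned the higher dose, which may be smaller than the effect of taking it. The document is written in the past tense, so if this analysis is applied after the data were seen it should be labelled post hoc.

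### Group B patients with side effects can move to group A after randomisation, and the readable SAP has no rule to analyse patients as assigned

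*Combined protocol and SAP*

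**What the plan says.** The aim is the effect of different metformin doses on the intermediates of NO biosynthesis. Item 6 of the Methods starts with a common lead-in ("Patients with pre-DM were treated 3 weeks with an increasing dose") and then assigns patients at random to group A (3 x 500 mg) or group B (3 x 1000 mg). Item 7 covers side effects in group B: "the patients could take a lower dose (3 x 500 mg if well-tolerated) and thus change to group A". The flow chart also places its tolerance branch ("Good dose tolerance: YES", with a NO arm) below the randomisation step. Where the NO arm leads cannot be read, because the figure is lost.

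On analysis, item 12 (SAP) says of the dose question only that "the difference of these compounds between two groups was done". It adds a baseline check: "to prove the homogeneity of the compared groups, analysis of the baseline parameters was done". The readable text does not define the groups as assigned or as taken, names no analysis set, has no rule for patients who step down, and asks for no count of them.

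Two other provisions bear on the point. Item 8 removes patients: "If the smallest dosage (3 x 500mg) was not tolerated the patient was excluded from the study". For group B, item 6 adds that "after 12 weeks this group returned to the dose 3 x 500 mg for the next 3 weeks", and the flow chart shows "3 weeks continuation of the dose 1500mg/day" before the final visit, so week 15 is not a contrast of the two doses.

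**The concern.** Randomisation makes groups comparable only if patients are analysed where they were assigned. Item 7 moves patients because of something that happens after assignment, and only from B to A. If poor tolerance goes with a higher or lower level of a compound, group B loses those patients and group A gains them, so both means shift. A difference can then appear with no dose effect, or a real one can look smaller or larger.

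The baseline check does not repair this. It covers measured baseline variables, not tolerance, and on the natural reading it would be applied to groups already re-formed. The dose comparison is the study's central analysis, and from the SAP alone a reader cannot tell whether it is a randomised one.

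**Working it through.** The plan gives no sample size, allocation ratio, switch rate, SD or effect size, so it has no figure to reproduce. Its only design number is the 0.05 significance level. Everything below is an illustration on the reading that switchers count in A.

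**Assumed inputs.** 1:1 allocation; n = 20, 30 or 50 per arm; share of B that switches p = 0.1, 0.2, 0.3; correlation r of intolerance with the outcome = 0, 0.1 or 0.3; outcome in SD units. Intolerance is standard normal, and B patients above z1 = Φ⁻¹(1 − p) switch.

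**Bias with no true dose effect.**
- Mean of the patients left in B: −r·φ(z1)/(1 − p)
- Mean of A including switchers: r·φ(z1)/(1 + p)
- Difference A − B: 2r·φ(z1)/(1 − p²)

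For p = 0.1, 0.2, 0.3, φ(z1) = 0.1755, 0.2800, 0.3477. At r = 0.3:
- 2 × 0.3 × 0.1755/0.99 = 0.106 SD
- 2 × 0.3 × 0.2800/0.96 = 0.175 SD
- 2 × 0.3 × 0.3477/0.91 = 0.229 SD

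At r = 0.1 the bias is one third of this: 0.035, 0.058, 0.076 SD. At r = 0 it is zero.

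**Type I error** (%, nominal 5% Welch t test, 40,000 simulated trials per cell):

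| r | n per arm | p = 0.1 | p = 0.2 | p = 0.3 |
|---|---|---|---|---|
| 0.1 | 20 | 5.0 | 5.4 | 5.5 |
| 0.1 | 30 | 5.0 | 5.7 | 5.9 |
| 0.1 | 50 | 5.2 | 5.8 | 6.5 |
| 0.3 | 20 | 6.1 | 8.0 | 10.0 |
| 0.3 | 30 | 6.6 | 9.7 | 13.1 |
| 0.3 | 50 | 8.1 | 13.7 | 19.4 |

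At r = 0, and by assigned group in every cell, it is 4.8–5.2%.

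**Second model.** Let a share s of patients be intolerant, with mean shifted by d SD, and let all intolerant B patients be counted in A. The bias of B − A is −2sd/(1 + s). At s = 0.2, d = 0.5 this is −0.2/1.2 = −0.167 SD, with type I error 7.7% at n = 20 and 12.5% at n = 50 (pooled t test, 20,000 trials). The pattern is the same.

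**With a true effect of 0.5 SD (B − A).** At r = +0.3 the expected estimate is 0.5 − 0.106, 0.5 − 0.175, 0.5 − 0.229 = 0.394, 0.325, 0.271 SD. At r = −0.3 it is 0.606, 0.675, 0.729 SD. Simulation agreed within its error.

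**Change from baseline.** Samples were taken before the first dose. If tolerance is linked to the compound only through a stable trait, comparing changes removes the bias (type I error 4.9–5.1%, assumed baseline to follow-up correlation 0.6). If tolerance is linked to the response itself, it does not (8.3, 13.4, 19.4% at n = 50, r = 0.3). The SAP does not say whether levels or changes are compared.

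**Item 8 exclusions after randomisation.** Let the least tolerant share f of switchers leave, with z2 = Φ⁻¹(1 − fp) and r = 0.3.
- Switchers in A: r[φ(z1)/(1 − p) + (φ(z1) − φ(z2))/(1 + p(1 − f))]
- By assigned group: r·φ(z2)/(1 − fp)

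| f | Analysis | p = 0.1 | p = 0.2 | p = 0.3 |
|---|---|---|---|---|
| 0.1 | Switchers in A (SD) | 0.099 | 0.164 | 0.215 |
| 0.1 | As assigned (SD) | 0.008 | 0.015 | 0.021 |
| 0.5 | Switchers in A (SD) | 0.079 | 0.133 | 0.179 |
| 0.5 | As assigned (SD) | 0.033 | 0.058 | 0.082 |

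At f = 0.5 and n = 50, type I error is 6.6, 9.7, 13.0% with switchers in A and 5.2, 5.9, 6.7% as assigned. f = 0.5 is probably extreme, since patients had been titrated to 3 x 500 mg before randomisation.

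**The case against.** The best reply is that the documents show exposure to bias, not bias. Item 7 sits among the treatment rules, and its wording may mean a change of regimen only. The lost figures might hold a rule or a count. Known gastrointestinal disease that could cause intolerance is excluded, everyone is titrated to the lower dose before assignment, and the higher dose is also reached by titration. All this makes a large switch share less likely. The highest error rates need p of 0.2 to 0.3, r = 0.3 and 50 per arm together.

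The as-assigned analysis also answers a somewhat different question from the stated aim. With a true effect of 0.5 SD it falls short of the full-dose effect by 0.05, 0.10, 0.15 SD. The dose-taken error is smaller than that at r = 0.1 (0.035, 0.058, 0.076) and larger at r = 0.3 (0.106, 0.175, 0.229).

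Much of this stands. The size is unknown, the missing count is the weaker half of the point, and which estimate lies nearer the full-dose effect depends on an unknown r. None of it supplies the missing rule. Item 7 is the only readable text on where a switcher belongs, and it points to A. Of the two analyses, only the one by assigned group keeps the null test valid whatever r is, apart from the residual due to item 8.

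**Conclusion.** The concern holds. Followed as written, items 6 and 7 with the SAP most naturally give a comparison of groups re-formed by tolerance, and nothing in the readable text says otherwise. Confidence is high on the missing rule; the consequence ranges from negligible to serious. It is nil if nobody switched, if tolerance is unrelated to the compounds, or if switchers were in fact kept in B. It is slight at a correlation of 0.1. At 0.3, type I error is 6–10% with 20 per arm and 8–19% with 50 per arm. Switch share, correlation and arm size are all assumed. The importance rests on the missing rule, because without it the main result cannot be identified as a randomised comparison.

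**What to change.** Leave the step-down option and item 7 as they are. Two additions to the SAP are essential:

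- Group labels for analysis are those assigned at randomisation. Every randomised patient with a sample is included in the assigned group, whatever dose was taken.
- The number who stepped down and the number excluded after randomisation are reported by assigned arm.

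Supporting changes:

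- Make week 12 the main dose comparison, since it precedes group B's scheduled return to 3 x 500 mg, and state whether levels or changes from baseline are compared.
- Analyse week 15 by assigned group as a separate comparison. Do the same for week 6 if it proves to follow randomisation.
- Keep the comparison by dose taken as a labelled sensitivity analysis.
- Reconcile the time of randomisation. Item 6 puts it after the 3-week lead-in, without saying immediately; the flow chart lists a control visit before it. The two may be compatible, but item 8 exclusions cannot be counted as before or after randomisation until this is settled.

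The text is in the past tense, so this would be a disclosed reanalysis rather than prespecification. It needs a few sentences and one rerun on samples already collected, with no new visits.

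The price is dilution: a true effect shrinks to about 0.9, 0.8, 0.7 of its size at p = 0.1, 0.2, 0.3. If tolerance is unrelated to the compounds, power for an assumed 0.8 SD effect with 30 per arm is about 77, 66, 54%, against 86, 84, 82% by dose taken. Patients excluded without a later sample can only be counted, which leaves the residual bias shown above.
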